**Recruitment:**

Patients will be identified from the surgical schedule the day before surgery and will be contacted by one of the study investigators to scan for eligibility for enrollment. Study aims and procedures will be explained to patients. Patients will be consented the morning of their surgery by one of the study investigator or the research coordinator.

25 patients will be enrolled in each study group with a total of 50 patients. Patients will be randomized to one of two study groups.

Group A will be named SS group, group B will be named the continuous infraclavicular block (CICB) group.

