**Randomization:**

A computer generated randomization table will be used for patient allocation to one of the two study groups; The SS group, or the CICB group. Randomization will be done in blocks of 10 patients. Patients' assignments will be written in a sealed envelope that is only open after patient consent for the study.

The study will be unblinded. Patients, nurses in the recovery room, and the research coordinator will be aware of the nature of patient assignment. **Currently, most patients presenting with distal radius fracture at PPMC will receive a single shot brachial plexus block for intraoperative anesthesia. We offer the continuous block option to patients with history of chronic pain or previous adverse reactions to oral opioids. Also these practices may vary depending on surgeon and anesthesiologist preference. Access to analgesic medications will not be restricted by any means for both study groups because of the study procedures.**

**Statistical Analysis:** Statistical analyses will be preformed using STATA 13 statistical software, Dallas, TX. Demographic data will be analyzed using student's T test or fisher's exact test as appropriate. Repeated measurements (pain scores) will be analyzed by repeated measures ANOVA or ANOVA on ranks, with further paired comparisons at each time interval performed using the t-test or Mann-Whitney U-test as appropriate. Categorical data will be analyzed using X analysis or Fisher's exact test where

applicable. Normally distributed data will be presented as means  $\pm$  SE of the mean (SEM), non normally distributed data are presented as medians  $\pm$  quartiles (interquartile range) and categorical data will be presented as raw data and as frequencies. The  $\alpha$  level for all analyses was set as  $P<0.05$ .

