**Sample Size Calculation:** A power analysis done prior to enrollment showed that the number of patients needed to detect a 1-point change in pain score ( $p<0.05$  significance level) was thirty-eight patients. While a 1-point change in pain score may not be clinically significant, we wanted the study to have enough power to detect between a 1-2 point pain score difference. Assuming a dropout rate of 20%, we will enroll fifty patients. Sample size estimate followed a previously published study comparing single shot versus continuous popliteal block for pain control after ankle fracture (5).

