#### **Measurements:**

- 1- Visual analogue scores every 8 hours for 72 hours after surgery. Pain scores will be recorded by patients in a pain diary
- 2- Measure opioid requirements for the first 3 days after surgery
- 3- Measure patient satisfaction with their pain management.
- 4- Measure the quality of recovery at 24 and 72 hours
- 5- Measure the quality of sleep in the first two nights after surgery. sleep quality questionnaire is adapted from the insomnia severity index (6) and we added

another questions asking about the frequency of waking up at night because of pain after surgery (7, 8)

6- Functional outcomes will be assessed at 3 months follow up during the office visit or through administration of the quick disability assessment of shoulder and hand (DASH) questionnaire (9), range of motion of the wrist and fingers will be recorded.

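### Does the sample-size paragraph need to change because the 38 patients cannot be reproduced from the inputs it states?

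*Combined protocol and SAP*

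**What the plan says.** The combined protocol and SAP justifies its size in one paragraph, Sample Size Calculation. It reports a power analysis giving "the number of patients needed to detect a 1-point change in pain score" as thirty-eight at p<0.05. It then concedes: "While a 1-point change in pain score may not be clinically significant", and explains that "we wanted the study to have enough power to detect between a 1-2 point pain score difference". A 20% dropout rate takes the number to fifty. On the source it says: "Sample size estimate followed a previously published study comparing single shot versus continuous popliteal block for pain control after ankle fracture".

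Under Recruitment, "25 patients will be enrolled in each study group with a total of 50 patients". Under Measurements, the pain outcome is "Visual analogue scores every 8 hours for 72 hours after surgery", which makes nine scores per patient if they are taken at 8, 16, ..., 72 hours. Under Statistical Analysis, "Repeated measurements (pain scores) will be analyzed by repeated measures ANOVA or ANOVA on ranks", followed by a t-test or Mann-Whitney test at each interval. On presentation, "Normally distributed data will be presented as means" with the standard error of the mean, and other data as medians with quartiles. The alpha level is 0.05; sidedness is not given.

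**The concern.** A two-group sample size for a mean needs a target difference, an SD, an alpha with its sidedness, and a power. Of these the paragraph gives only the difference and alpha. It names the pain score but not the time point or summary, although the diary yields several readings. It points to a trial of a different block and operation and restates no SD or power from it. It also casts doubt on the importance of 1 point and then speaks of a range of 1 to 2 points, which reads as if no target had been settled.

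If the true SD were well above the one behind the 38, the trial could miss the difference it was sized for. Lower pain scores come first in the study hypothesis, so a non-significant pain result would be hard to interpret if the design had little power.

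**Working it through.** **Inputs from the document.** Difference 1 point, extended in words to 1-2 points; alpha 0.05; 38 patients; dropout 20%; 50 enrolled, 25 per group; allocation 1:1 (Study design). Power, SD and sidedness are not given.

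**Step 1: the plan's own figure.** The 38 cannot be reproduced without an SD and a power. The dropout step can: 38/(1 − 0.20) = 47.5, so 48, and 50 are enrolled. Fifty also fills five randomisation blocks of 10. This step supports reading 38 as a two-arm total, 19 per arm, because 38 per arm would be 76 and exceed enrolment.

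**Step 2: the SD that 38 implies.** Assume a two-sample t-test, two-sided alpha 0.05 and 80% power. With 19 per arm the noncentrality needed is 2.879, so the detectable standardised difference is 2.879 × √(2/19) = 0.934. The largest SD is then 1/0.934 = 1.07 for 1 point and 2/0.934 = 2.14 for 2 points. Other assumptions move these limits:

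| Assumption | 1 point | 2 points |
|---|---|---|
| two-sided, 80% power | 1.07 | 2.14 |
| two-sided, 90% power | 0.93 | 1.85 |
| one-sided, 80% power | 1.22 | 2.43 |
| one-sided, 90% power | 1.03 | 2.07 |
| Mann-Whitney, two-sided, 80% power | 1.04 | 2.09 |

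**Step 3: power with 40 evaluable.** 50 × 0.80 = 40, or 20 per arm. Two-sided t-test, SDs assumed:

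| SD | 1 point | 2 points |
|---|---|---|
| 1.07 | 82% | >99% |
| 1.5 | 54% | 98% |
| 2.0 | 34% | 87% |
| 2.5 | 23% | 69% |

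**Step 4: the score matters too.** The mean of nine scores with within-patient correlation r has SD equal to the per-score SD × √((1 + 8r)/9). With a per-score SD of 1.5 and r = 0.5 (assumed), that is 1.5 × 0.745 = 1.12, and power for 1 point is 79% instead of 54% at a single time point. For r from 0.3 to 0.7 it runs from 92% to 67%.

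**Step 5: one target or two?** The 38 is tied to one effect, 1 point. At any given SD, a trial with adequate power for 1 point has more for 1.5 and 2. At SD 1.07, 80% power needs 19 per arm for 1 point and 6 for 2 points. The second sentence can therefore be read as choosing the demanding end of the range on purpose.

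**Step 6: what the report will show.** With normally distributed scores, group means and their standard errors are planned. The standard error of the difference is √(SEM₁² + SEM₂²). With 20 per arm and SD 1.5 (assumed), each SEM is 1.5/√20 = 0.335, the SE of the difference is 0.474, and the 95% half-width is 2.024 × 0.474 = 0.96 points. A reader can form this interval whatever power was planned.

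**The case for a change.** The best case for a change is that this paragraph is the only justification for the size of the trial, that it leaves out inputs the sponsor should already hold, and that a few sentences would supply them. The cited trial does not help a reader who has only this document. If the SD is 1.5 or more, power for 1 point at a single time point is 54% or lower, and at SD 2.5 even a 2-point difference is missed in 31% of trials. The rank-based route reports medians and quartiles, from which a confidence interval for the difference cannot be rebuilt.

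The omission is real, and so is the limitation of the median route. The rest does not carry a change. The SDs of 1.5 to 2.5 are illustrations without a source in the documents, and the lowest power figures apply to one time point tested alone with the full 20% lost, whereas the plan analyses the scores jointly as repeated measures. Supplying the missing inputs would leave the same 50 patients, diary and tests. The changes that would alter the trial are not supported. Enrolling more needs an SD that shows a shortfall, and naming 2 points because 50 patients then suffice would fit the target to the number. A confidence interval for the difference is a sensible addition to the report, and the analysts can give it without amending the plan.

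**Conclusion.** The concern does not lead to a change. The paragraph omits the power, the SD, the sidedness and the time point or summary of the pain score, so 38 cannot be checked, but nothing in the documents shows that it is wrong. The dropout arithmetic holds (47.5, enrolled as 50), the 38 rests on a single stated effect of 1 point, and power for that effect covers larger ones.

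The size of the uncertainty is an implied SD limit of 1.07 for 1 point and 2.14 for 2 points (1.22 and 2.43 if one-sided). This rests on reading 38 as a two-arm total, a t-test and 80% power. Whether the true SD lies above or below these limits cannot be decided from the documents. A non-significant result would still be interpretable from the observed difference and its precision, directly where means and standard errors are reported and less easily where medians are. This is a gap in reporting that analysts can fill from the calculation already done, not an arithmetic error or a defect in the design.

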#### **Study duration:**

We plan to begin enrollment in October 2015. The enrollment of all subjects is projected to be completed in October 2016 with data analysis to follow. The study is expected to be completed by January 2017. The length of participation for each subject will be three months total – 3 months as follow up data will be collected during the follow up office visits.

#### **Measurements:**

- 1- Visual analogue scores every 8 hours for 72 hours after surgery. Pain scores will be recorded by patients in a pain diary
- 2- Measure opioid requirements for the first 3 days after surgery
- 3- Measure patient satisfaction with their pain management.
- 4- Measure the quality of recovery at 24 and 72 hours
- 5- Measure the quality of sleep in the first two nights after surgery. sleep quality questionnaire is adapted from the insomnia severity index (6) and we added

another questions asking about the frequency of waking up at night because of pain after surgery (7, 8)

6- Functional outcomes will be assessed at 3 months follow up during the office visit or through administration of the quick disability assessment of shoulder and hand (DASH) questionnaire (9), range of motion of the wrist and fingers will be recorded.

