### **Study Objectives:**

- 1- Measure visual analogue scores every 8 hours for 72 hours after surgery. Pain scores will be recorded by patients in a pain diary (see appendix)
- 2- Measure opioid requirements for the first 3 days after surgery
- 3- Measure patient satisfaction with their pain management.
- 4- Measure the quality of recovery (QOR) at 24 and 72 hours. using the QOR-9 questionnaire.( see appendix)
- 5- Measure the quality of sleep in the first two nights after surgery using a sleep questionnaire ( see appendix)
- 6- Functional outcomes will be assessed at 3 months follow up during the office visit or through administration of the disability assessment of shoulder and hand questionnaire, range of motion of the wrist and fingers will be recorded. (see appendix)

This study tests the hypothesis that patients receiving continuous ICB will have lower pain scores, will use less opioids, will sleep better the first two nights after surgery and will be more satisfied with their pain control regimen after surgery.

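### An 8-hourly self-completed pain diary, taken literally, schedules about one reading in most patients' sleep each night, and the plan does not say what a sleeping patient should do

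*Combined protocol and SAP*

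**What the plan says.** Study Objectives (item 1) and Measurements (item 1) set the same schedule: "Visual analogue scores every 8 hours for 72 hours after surgery. Pain scores will be recorded by patients in a pain diary". Measurements (item 5) adds a second self-reported outcome over part of the same period: "Measure the quality of sleep in the first two nights after surgery". For that outcome, the "sleep quality questionnaire is adapted from the insomnia severity index", and the investigators add "another questions asking about the frequency of waking up at night because of pain after surgery". Lower pain and better sleep on those two nights are both in the study hypothesis that closes Study Objectives.

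The Statistical Analysis paragraph states that "Repeated measurements (pain scores) will be analyzed by repeated measures ANOVA or ANOVA on ranks", followed by comparisons at each time interval.

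The text available does not say whether the 8-hour intervals start at the end of surgery or follow fixed clock hours. Nor does it say how far a reading may move, what to do when one falls during sleep, how to mark a late entry, or how missing scores are analysed. The diary and the sleep questionnaire are in an appendix that is not part of the text reviewed.

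**The concern.** Because 24 is a multiple of 8, an 8-hourly schedule does not drift around the clock. A patient whose grid includes a reading at 03:00 has one at 03:00 on all three nights. That patient can do one of three things, and each touches an outcome.

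- **Wake to score.** This adds awakenings unrelated to pain during the two nights on which sleep is assessed, in both arms.
- **Leave it blank.** A patient already awake with pain can record a score and a comfortable sleeper cannot, so blanks may depend on the value that is missing.
- **Fill it in later.** The score becomes recall, with no date or time to distinguish it from a real-time score.

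If the continuous block works as hypothesised, its low night scores would be the likelier ones to go missing, and the recorded night difference would understate the true one. The Sample Size Calculation aims at a difference of 1 to 2 points, so a loss of a few tenths of a point matters.

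**Working it through.** **1. The plan's own figures.** 72 / 8 = 9 scheduled readings (8, 16, ..., 72 hours) over three nights. The sample size of 38, inflated for 20% dropout, is 38 / 0.80 = 47.5, so 48; the plan enrols 50, which leaves 50 × 0.80 = 40. Nothing in that calculation depends on the diary schedule.

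**2. How often a reading falls in sleep.** Assumption: readings run from the end of surgery. If that time is spread evenly over the 8-hour cycle, the share of patients with a reading inside a sleep of L hours (L up to 8) is L / 8: 75%, 87.5% and 100% for 6, 7 and 8 hours.

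With end of surgery assumed even over 09:00-18:00 (9 hours):

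- Sleep 00:00-06:00: only ends between 14:00 and 16:00 avoid it, so 1 − 2/9 = 78% are affected.
- Sleep 23:00-06:00: only ends between 14:00 and 15:00 avoid it, so 1 − 1/9 = 89%.
- Sleep 23:00-07:00: 100%, apart from the boundary case of an end at exactly 15:00.

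Examples: an end at 12:00 gives 20:00, 04:00 and 12:00 every day. An end at 14:00 gives 22:00, 06:00 and 14:00, with none strictly inside a 22:00-06:00 night.

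**3. Effect of a tolerance window.** If a reading may move by w hours either way, the share under the even-cycle assumption is (L − 2w) / 8.

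| Sleep | w = 0 | w = 1 h | w = 2 h |
|---|---|---|---|
| 6 h | 75% | 50% | 25% |
| 7 h | 87.5% | 62.5% | 37.5% |
| 8 h | 100% | 75% | 50% |

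**4. Effect of selective blanks on the pain difference.** Every input here is assumed. Night pain is normal with mean 5 (single shot) and 3 (continuous), SD 2.5, clipped to 0-10, which gives a true difference of 1.86. The chance of recording a score x is 1 / (1 + exp(−s(x − c))), with centre c from 3 to 5 and slope s. The recorded mean in each arm is E[x·p(x)] / E[p(x)]. For the nine-reading average, the six day readings are complete and carry the same true difference: (6 × 1.86 + 3 × night difference) / 9.

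| Slope s | Night difference seen | Average over nine readings |
|---|---|---|
| 0.25 | about 1.80 | 1.84 |
| 0.5 | 1.58 to 1.52 | 1.77 to 1.75 |
| 1.0 | 1.24 to 1.04 | 1.65 to 1.59 |

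At s = 1.0, 50-74% of single-shot and 26-50% of continuous-block night scores are recorded. That slope multiplies the odds of recording by exp(1) = 2.7 per pain point and is a steep case.

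**5. Effect of blanks on the number analysed.** If the repeated measures ANOVA uses only patients with every reading, and each of three night readings is missed independently with probability q, the share kept is (1 − q)³: 73%, 34% and 13% at q = 10%, 30% and 50%. Of 40 patients that is about 29, 14 and 5, against the 38 the plan says it needs. The plan does not say that incomplete patients are dropped; it does not say what happens to them.

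**The case against.** The strongest reply is that the start of the intervals is not stated. The wording may describe the 72-hour window rather than a clock that starts when surgery ends. Fixed hours such as 22:00, 06:00 and 14:00 satisfy it with no reading strictly inside an 8-hour night. The diary form is in the unseen appendix and may print times, a late-entry rule or an instruction not to wake. This stands as a limit on certainty. A grid that runs from surgery remains the natural reading, and the available text does not fix the hours.

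A reader might infer that the diary must either spoil the sleep outcome or lose night scores according to pain. The documents do not support that. Late entry is a third route, some patients will be awake, and nothing in the plan shows that recording depends on pain.

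A reader might also infer that the sleep comparison is biased. Both arms share the schedule, so waking to score would mainly lower sleep quality in both. The added item asks about waking because of pain, which waking to score is not. A smaller sleep difference is possible but has not been shown.

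Nor can the lost scores be tied to the hours when single-shot blocks wear off: the documents give no block duration.

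Finally, the illustration depends heavily on the slope. At 0.25 the loss is negligible, and only a third of the readings are exposed. That is correct, and the range should be read as a whole.

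**Conclusion.** The point holds as a weakness in the measurement schedule. On the natural reading, about one diary entry falls in each night's sleep for most patients: about 78-100% for 6 to 8 hours of sleep with surgery ending 09:00-18:00 and no tolerance, and fewer with one. About 3 of 9 scores are exposed in those patients.

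The consequences are conditional. If recording rises with pain, the bias in the pain difference is toward zero: from about 0.06 (1.86 to 1.80) to about 0.8 points (1.86 to 1.04) at night, and from about 0.02 to 0.27 points over all nine readings. These sizes rest on assumed means, SD and slopes, not on trial data. If diaries are incomplete and the ANOVA uses complete cases only, the loss of patients could matter more than the bias.

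This is worth settling before enrolment, because the schedule can be changed cheaply then and missing night scores cannot be recovered afterwards. The conclusion is subject to what the diary appendix says.

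**What to change.** In Study Objectives (item 1) and Measurements (item 1), replace the 8-hour grid with three waking readings a day through 72 hours: on waking, mid-afternoon and bedtime. Have the patient write the actual time beside each. Add one item on waking for worst pain overnight, reported separately from the current-pain scores. State in the diary that patients should not wake to score. The sleep questionnaire stays as planned.

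In Statistical Analysis, compare the arms by diary occasion or by actual hours since surgery, using an analysis that keeps patients with incomplete diaries, for example a mixed model. Such a model does not by itself remove bias from blanks that depend on unrecorded pain, so add a sensitivity analysis for missing scores.

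The cost is diary and protocol wording plus a revised analysis paragraph. The number of current-pain readings per day is unchanged. The downsides are that readings are no longer exactly 8 hours apart or aligned to hours since surgery, and that the overnight value is recalled by patients who know their assignment. If the appendix already sets times and a rule for sleep, bring that rule into the protocol text and limit the change to what it leaves open.

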### **Methods:**

**Study design:** prospective, randomized, unblinded study with a parallel design and an allocation ratio of 1 to 1 for the treatment groups.

**Inclusion Criteria:** Patients scheduled for open reduction and internal fixation of a distal

radius fracture with American Society of Anesthesiologists (ASA) physical status I -III, mentally competent and able to give consent for enrollment in the study.

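### No pre-block pain score is listed and no covariate is named, so the pain comparison in about 40 evaluable patients cannot be adjusted for starting pain: a modest loss of precision, not a bias, and cheap to avoid.

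*Combined protocol and SAP*

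**What the plan says.** Study Objectives, item 1, sets the pain outcome as "Measure visual analogue scores every 8 hours for 72 hours after surgery". Measurements, item 1, repeats it and names the source: "Visual analogue scores every 8 hours for 72 hours after surgery. Pain scores will be recorded by patients in a pain diary". Every listed score is post-operative. The diary itself is in an appendix that is not part of the available text.

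The Statistical Analysis paragraph states "Repeated measurements (pain scores) will be analyzed by repeated measures ANOVA or ANOVA on ranks", followed by t-tests or Mann-Whitney tests at each time. It names no covariate.

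Under Recruitment, "Patients will be consented the morning of their surgery by one of the study investigator or the research coordinator". The Randomization section has the sealed envelope opened only after consent, and Study procedures places consent ahead of sedation and block. A contact therefore already exists at which pain could be scored without knowledge of the arm.

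No outcome is labelled primary. Pain is objective 1, comes first in the hypothesis and is the basis of the sample size, so treating it as the main comparison is a fair reading.

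**The concern.** These patients have a fracture, and some will be in more pain than others before surgery. If that starting pain predicts the diary scores, part of the between-patient spread in the diary could be explained and removed from the error term. With about 20 evaluable patients per arm and a target difference of 1 to 2 points, such a gain could matter.

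The omission also cannot be repaired later. A covariate can be added to an analysis plan up to the point of analysis, but a pre-block score cannot be collected once the block is in. In an open-label trial with self-reported pain, a score taken before the envelope is opened is also the only pain rating that cannot reflect knowledge of the assignment. Finally, Study procedures provides for withdrawal after a failed or misplaced catheter, a route that applies to the continuous arm. Without a baseline score nobody can check whether the patients who remain started at similar pain levels.

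**Working it through.** **Inputs from the plan.** Allocation is "an allocation ratio of 1 to 1 for the treatment groups" (Study design). Enrolment is 25 per arm, 50 in total (Recruitment). The Sample Size Calculation says that "the number of patients needed to detect a 1-point change in pain score" at the 0.05 level "was thirty-eight patients", and assumes 20% dropout. It gives neither an SD nor a power. Sidedness is not stated; two-sided 0.05 is assumed here.

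**The plan's own figures.**
- Dropout: 38 / 0.8 = 47.5, so 48, against 50 planned, which is close enough. Evaluable: 50 × 0.8 = 40, or 20 per arm.
- The 38 cannot be reproduced without an SD and a power. Solving backwards for 19 per arm, a 1-point difference, 80% power and two-sided 0.05: SD = √(19/2) / (1.960 + 0.842) = 3.082 / 2.802 ≈ 1.10.

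**Net effect of adjustment.** Adjusting for a baseline score with correlation r multiplies the residual variance by (1 − r²). Estimating the covariate at N = 40 costs a factor of about 1 + 1/36 = 37/36. The net variance factor is V = (1 − r²) × 37/36, and the equivalent unadjusted sample is 40 / V. The documents do not give r, so a range is assumed.

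| r | V | Change in variance | Equivalent N |
|---|---|---|---|
| 0.1 | 0.99 × 37/36 = 1.017 | +2% | 39.3 |
| 0.2 | 0.96 × 37/36 = 0.987 | −1% | 40.5 |
| 0.3 | 0.91 × 37/36 = 0.935 | −6.5% | 43 |
| 0.4 | 0.84 × 37/36 = 0.863 | −14% | 46 |
| 0.5 | 0.75 × 37/36 = 0.771 | −23% | 52 |
| 0.6 | 0.64 × 37/36 = 0.658 | −34% | 61 |

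Break-even is where 1 − r² = 36/37, so r = √(1/37) ≈ 0.16.

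**Power.** This is a two-sample t calculation at a single time point with 20 per arm: noncentrality δ / (SD × √V × √(2/20)), with 37 degrees of freedom when adjusted. Unadjusted, V = 1 and there are 38.

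| Scenario | Unadjusted | r = 0.2 | r = 0.3 | r = 0.5 | r = 0.6 |
|---|---|---|---|---|---|
| 2 points, assumed SD 2 | 87% | 87% | 89% | 94% | 97% |
| 1 point, back-solved SD 1.10 | 80.0% | 80.5% | 82.5% | 89% | 93% |

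**Chance imbalance.** At an assumed SD of 2, the chance difference in mean baseline pain between arms has SD 2 × √(2/20) = 0.63 point. Only the share r of that reaches the outcome when baseline and outcome SDs are equal: 0.2 × 0.63 = 0.13, 0.3 × 0.63 = 0.19 and 0.5 × 0.63 = 0.32 point.

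**The case against.** The strongest objection is that a useful r is doubtful here. Both arms receive the same initial block, the catheter arm then has an infusion with patient boluses, opioids are taken as needed, and access to analgesics is unrestricted. The diary therefore records treated pain after fixation, whereas a morning score records fracture pain before it. The gain is material only from about r = 0.4, and nothing in the documents shows that r is that high. This stands as a limit on the size of the gain. It does not defeat the proposal: even if r is zero the cost is 1/36, just under 3% of variance, while r of 0.3 to 0.5 would return 6.5% to 23%.

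Three further limits stand. The power figures treat one time point, whereas the plan analyses up to nine scores (72 / 8) together. The plan allows a rank-based analysis, so a covariate must be specified for that branch too. And the unseen diary could contain a pre-operative line, so the supportable statement is that none is listed in the visible text.

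A reader might infer that chance differences in starting pain bias the trial, or carry over in full, so that 0.63 point could be set against a 1-point target. Neither follows. Assignment is randomized, the unadjusted standard error already includes this variation, and only the share r carries through. A reader might also blame the missing baseline for low power: at an assumed SD of 2, unadjusted power for 1 point is about 34%. That figure comes from the assumed SD, and adjustment at r = 0.6 would raise it only to about 48%. The unstated SD and power are a separate and larger gap.

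**Conclusion.** The point holds as a minor one about precision. On the visible text, the pain comparison cannot be adjusted for starting pain, because no pre-block score is listed and no covariate is named. The planned unadjusted comparison is not made invalid by this.

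What is given up ranges from nothing (r below about 0.16) through a modest amount (6.5% of variance at r = 0.3, about 3 patients' worth) to a useful one (23% at r = 0.5, about 12 patients' worth in a trial of 40 evaluable). The result rests on an assumed r, two-sided 0.05, 20 evaluable per arm and a single-time-point approximation. The power figures also need an SD, either assumed at 2 or back-solved at about 1.1 on the further assumption of 80% power. The documents support saying that some precision may be lost; they do not support a specific amount.

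**What to change.** Two additions, made together, since a baseline score adds no precision unless the analysis uses it.

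- Measurements, item 1: *VAS is also recorded once on the morning of surgery, after consent, before the allocation envelope is opened and before any sedation or block.*
- Statistical Analysis: *Baseline VAS is a covariate in the pain-score model and in the comparisons at each time point (ANCOVA, or rank-based ANCOVA if ranks are used).*

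If the diary appendix already has a pre-operative line, only its timing relative to the envelope and the covariate statement need adding.

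The cost is one extra mark per patient at an existing contact and one degree of freedom, with little or no gain, or a loss of about 2% to 3% of variance, if r is low. No visit, staff or clinical procedure changes.
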